3.3.4.2 Withdrawal of consent to trial participation

Patients may withdraw their consent to trial participation at any time without the need to justify the decision.

If a patient wants to withdraw consent, the investigator should be involved in the discussion with the patient and explain the difference between trial treatment discontinuation and withdrawal of consent to trial participation, as well as explain the options for continued follow-up after trial treatment discontinuation, please see section [3.3.4.1](#) above.

3.3.4.3 Discontinuation of the trial by the sponsor

Boehringer Ingelheim reserves the right to discontinue the trial overall or at a particular trial site at any time for the following reasons:

1. Failure to meet expected enrolment goals overall or at a particular trial site.
2. Emergence of any efficacy/safety information invalidating the earlier positive benefit-risk-assessment that could significantly affect the continuation of the trial.
3. Deviations from GCP, the trial protocol, or the contract impairing the appropriate conduct of the trial.

The investigator / the trial site will be reimbursed for reasonable expenses incurred in case of trial termination (except in case of the third reason).

4. TREATMENTS

4.1 INVESTIGATIONAL TREATMENTS

4.1.1 Identity of the Investigational Medicinal Products

Table 4.1.1: 1 BI 891065

Substance:	BI 891065
Pharmaceutical formulation:	Film-coated tablets
Source:	Boehringer Ingelheim Pharma GmbH & Co. KG
Unit strength:	5 mg, 20 mg, 50 mg, 100 mg tablets
Posology:	Once daily (q.d.) or twice daily (b.i.d.), individual dose depending on dose escalation
Method and route of administration:	Oral

Table 4.1.1: 2 BI 754091

Substance:	BI 754091
Pharmaceutical formulation:	Solution for infusion
Source:	Boehringer Ingelheim Pharma GmbH & Co. KG
Unit strength:	20 mg/mL (vial with 15 mL filling volume)
Posology:	Infusion on day 1 of 21-day cycles
Method and route of administration:	Intravenous infusion

4.1.2 Selection of doses in the trial and dose modifications

4.1.2.1 Starting dose of BI 891065

In Part A, BI 891065 will be tested at a starting dose of 100 mg once daily. In case of DLTs in 100 mg cohort, a lower dose level may also be investigated. Twice daily dosing may also be investigated.

The starting dose was selected based on the data obtained in clinical trial 1379-0001 monotherapy dose-escalation part. As of the end of January 2019, BI 891065 was administered at dose range of 5 mg to 400 mg in 25 patients as single agent. In these patient cohorts, DLTs were not reported at any dose level tested, and the MTD was not reached. There was no treatment related SAE. There was an isolated increase in total bilirubin in 7 patients (28%) which appears to be dose-dependent. All bilirubin increases were maximum Grade 2 and did not lead to dose-reduction or discontinuation of study drug. Twice daily dosing will be explored, aiming to reduce peak plasma concentrations compared to single dosing of the same daily dose, which may reduce occurrences of bilirubin increase, and may allow for better tolerability of similar total daily doses compared to once daily dosing, and potentially higher daily doses. Etiology and clinical significance are currently under further investigation. Otherwise there were no abnormal lab trends identified which could not be explained by underlying disease. To obtain sufficient dose-PK relationship data in Asian patients, the starting dose of this trial is set at a lower dose than the highest dose in trial 1379-0001.

In Part B, the starting dose of BI 891065 will be 200 mg per day, in combination with BI 754091 240 mg once every three weeks. The SMC may recommend to start at a lower dose level depending on the MTD or occurrence of DLTs in Part A. In case of DLTs in the starting dose cohort of Part B, a lower dose level may also be investigated. Twice daily dosing will also be investigated.

4.1.2.2 Dose of BI 754091

The dose of BI 754091 will be fixed at 240 mg once every three weeks. The dose of BI 754091 was selected based on the data from preceding trials, including a first-in-human Phase I trial in Western patients (Trial 1381-0001) and a Phase I trial in Asian patients (Trial 1381-0004).

In the dose escalation part of trial 1381-0001, dose levels of 80 mg, 240 mg, and 400 mg every 3 weeks were investigated and three patients were assigned at each cohort. None of them experienced DLTs and the MTD was considered not reached. The RD for further development was determined to be 240 mg based on the results of in vitro binding testing, clinical safety data and the result of a receptor occupancy testing in trial 1381-0001. The preliminary data showed 100% PD-1 receptor occupancy in peripheral blood in all on-treatment patient samples compared to baseline throughout one treatment cycle, which also supports that the selected dose of 240mg administered every 3 weeks should be adequate.

The clinical safety is further supported by the data from trial 1381-0004 dose-finding part, where six Japanese patients received BI 754091 monotherapy 240 mg every 3 weeks and none of them experienced DLTs (Median number of treatment cycles: 4.5, range 2-8).

4.1.3 Dose-finding scheme

The dose is planned to be tested in cohorts at pre-defined provisional dose levels. The provisional dose levels to be assigned to different cohorts of patients are listed in Tables [4.1.3: 1](#) and [4.1.3: 2](#). Intermediate or lower dose levels may be investigated if agreed in the SMC, depending on the number of DLTs observed in the trial. The highest planned dose of BI 891065 is 400 mg per day.

Table 4.1.3: 1 Example of dose escalation in Part A

Dose level	Proposed daily dose of BI 891065*	Participating countries
1	100 mg	Japan
2	200 mg **	Japan
3	400 mg **	Japan and Taiwan

*The total daily dose will be given in q.d. or b.i.d. dosing schedule.

**Actual dose level and dosing schedule for a cohort will be communicated separately as determined by the SMC. Intermediate or lower dose level(s) may be investigated depending on the latest DLT rate estimate.

Table 4.1.3: 2 Example of dose escalation in Part B

Dose level	Proposed daily dose of BI 891065*	Proposed dose of BI 754091 (every three weeks)	Participating countries
1	200 mg **	240 mg	Japan and Taiwan
2	400 mg **	240 mg	Japan and Taiwan

* The total daily dose will be given in q.d. or b.i.d. dosing schedule.

**Actual dose level and dosing schedule for a cohort will be communicated separately as determined by the SMC. Intermediate or lower dose level(s) may be investigated depending on the latest DLT rate estimate.

4.1.4 Method of assigning patients to treatment groups

There will be no randomisation in this trial, as it is a single-arm open-label trial.

An interactive response technology (IRT) system is used to register participation of patients in the trial. Upon acquisition of informed consent, study sites access the IRT to register patients for screening. After assessment of all inclusion and exclusion criteria, study sites access the IRT to register each eligible patient for treatment, and the IRT system will assign the patient to the cohort which is open for recruitment.

As soon as the planned number of patients in a cohort are registered for treatment, IRT will close the screening until the next cohort is opened for recruitment or until further treatment slots become available in the current cohort. Patients who are already in screening at the time of the closure of the screening and who then meet all eligibility criteria can be registered for treatment. If more patients are eligible than planned number of patients for a cohort, it is exceptionally allowed to register more patients than planned for ethical reasons.

4.1.5 Drug assignment and administration of doses for each patient

4.1.5.1 Administration of BI 891065

BI 891065 tablets must be stored in the containers provided and handled according to the labelled storage instructions and shelf life. Labels will be prepared in accordance with Good Manufacturing Practice (GMP) and local regulatory guidelines.

Patients need to be instructed to return any unused BI 891065 in the dispensed bottles, in addition to returning any empty bottles.

All patients will be required to complete a Dosing Diary, which must be returned to the clinic for review at each clinic visit. The fasting status on the PK days should be recorded in the patient diary and collected in the eCRF (section [5.3.1](#)). The diary should be given to patients before cycle 1 day 1.

Refer to [Flow Chart](#) and section [10.3](#) for information about sampling that is required prior to dose administration.

BI 891065 is taken either q.d. or b.i.d., depending on the assigned treatment regimen. Refer to [Flow Chart](#) for exceptions of dosing schedule where study drug is skipped.

Patients will be asked to fast overnight (minimum of 10 hours) prior to the morning dose on the following intensive PK days:

- Cycle 1 Day 1
- Cycle 1 Day 15

Refer to section [10.3](#) for details.

When BI 891065 and BI 754091 are to be administered on the same day, BI 891065 will be administered approximately 30 minutes following the end of infusion of BI 754091, based on the safety assessments made by the Investigator.

Whenever possible, all doses of BI 891065 should be taken with water, limited to a maximum of 240 mL.

Missed doses of BI 891065 should not be made up if more than 6 hours have passed since scheduled dosing time. Missed doses must be recorded in the patient's Dosing Diary, and then should be recorded in the eCRF.

4.1.5.2 Administration of BI 754091

Vials of BI 754091 will be diluted and administered via i.v. infusion according to the details in the Instruction for Pharmacists.

4.1.6 Dose modifications (pause, delay, dose reduction, and discontinuation)

AEs that are immune related should be managed according to the Guidelines for irAE management (as outlined in Appendix [10.2](#)).

For Grade 4 AE/SAEs that are not immune related, study drug should be withdrawn. However, if it can be excluded with high certainty that the event was related to study medication, study drug should be paused, and resumption of study drug may be allowed after discussion with the Sponsor.

For Grade 3 AE/SAEs that are not immune related, study drug should be paused.

For Grade 2 AEs/SAEs that are not immune related but are deemed intolerable by the patient or the treating physician and not responding to appropriate medical management, the physician should decide if a pause of treatment is warranted considering relevant variables such as perceived relatedness to study drug.

If, after a treatment pause of \leq 12 weeks, the non-immune related SAE/AE resolves to baseline or Grade 1 and the physician thinks it is clinically appropriate to restart study drug, then the physician may choose to restart BI 891065 at one dose lower than the dose administered before the pause (except for patients who are receiving the lowest dose allowed) according to Table [4.1.6: 1](#) and Table [4.1.6: 2](#), and BI 754091 at the same fixed dose of BI 754091. Up to two dose reductions of BI 891065 are allowed per patient. If the AE/SAE prompting interruption has unequivocally been excluded to be drug related, reintroduction of BI 891065 at the same dose as prior to the pause may be considered.

There will be no dose reductions or escalations of BI 754091 in any one patient. However, in the event of an infusion-related reaction \leq Grade 2, the infusion rate of BI 754091 may be decreased by 50% or interrupted until resolution of the event and re-initiated at 50% of the initial rate until completion of the infusion. In patients experiencing infusion-related reactions \leq Grade 2, subsequent infusions may be administered at 50% of the initial rate. If an infusion-related reaction is Grade 3 or higher in severity at any point during the study, treatment with BI 891065 and BI 754091 will be permanently discontinued.

As a general rule for Part B, both drugs (BI 891065 and BI 754091) will be stopped, paused, or re-exposed together. Exemptions have to be justified and aligned with the Sponsor in writing.

If exemption to the dose reduction and pause (e.g., to restart the treatment at the same dose level) is considered, it should be discussed and agreed with the sponsor in advance in writing.

Table 4.1.6: 1

Dose reduction recommendations for BI 891065 in q.d. dosing (up to two dose reductions are allowed per patient)

BI 891065 dose before the pause	BI 891065 dose at restart
400 mg	200 mg
200 mg	100 mg
100 mg	50 mg (lowest dose allowed)

Table 4.1.6: 2

Dose reduction recommendations for BI 891065 in b.i.d. dosing

BI 891065 dose before the pause	BI 891065 dose at restart
200 mg x 2	100 mg x 2
100 mg x 2	50 mg x 2 (lowest dose allowed)

If an intermediate dose which is not listed in the table is investigated, a dose reduction guideline for that dose will be provided separately

There will be no dose reductions or escalations of BI 754091. Modifications of infusion rate are described in section [5.2.6.1.4](#).

The study treatment should be permanently discontinued if any of the following adverse events occur:

- A pause of treatment or delayed start of treatment of more than 12 weeks due to AEs
- Grade 3 or 4 CRS
- Interstitial lung disease (ILD) of any grade
- (For Part B only) Immune related AEs requiring permanent study drug discontinuation as described in Guidelines for Management of Immune-Related AEs (section [10.2](#)):
 - encephalitis, aseptic meningitis, transverse myelitis, or Guillain-Barre syndrome of any grade
 - acquired thrombotic thrombocytopenic purpura of any grade
 - myocarditis of any grade
 - myasthenia gravis, peripheral neuropathy or autonomic neuropathy of grade ≥ 3
 - myositis grade 2 with objective findings (see below), any myositis grade ≥ 3
 - hepatitis grade ≥ 3 (transaminase >5 times ULN or total bilirubin >3 times ULN), recurrent hepatitis grade ≥ 2
 - nephritis grade ≥ 3 , persisting grade 2 nephritis unresponsive to initial steroid therapy or worsening, and recurrent nephritis grade ≥ 2
 - pneumonitis grade ≥ 3 ,
 - rash, bullous dermatoses, severe cutaneous adverse reaction, Stevens Johnson Syndrome, toxic epidermal necrolysis of grade 4, and recurrent rash grade ≥ 3
 - colitis grade 4, and recurrent colitis of any grade
 - uveitis, iritis, episcleritis of grade ≥ 3

Proprietary confidential information © 2021 Boehringer Ingelheim International GmbH or one or more of its affiliated companies

- autoimmune-hemolytic anemia grade ≥ 2
- haemolytic uremic syndrome grade ≥ 3
- immune thrombocytopenia grade 4
- any recurrent irAE grade ≥ 3
- inability to taper steroids to 10 mg or less prednisone or equivalent within 12 weeks, or
- persistent Grade 2-3 AEs that do not recover to Grade 1 or less within 12 weeks.
- Grade ≥ 3 infusion related reactions
- AEs of Grade ≥ 2 deemed intolerable by the patient or the treating physician and not responding to medical management within 12 weeks
- Grade 3 to 4 AEs that are classified as immune-related by the Investigator but are not listed in section [10.1](#) if they do not resolve to Grade ≤ 1 or baseline with immunosuppressive therapy within 2 weeks.
- \geq Grade 4 drug-related AEs.

Other criteria leading to permanent discontinuation of study treatment are presented in Section [3.3.4.1](#).

4.1.7 Dose limiting toxicities

Dose-limiting toxicities (DLTs) will be recorded throughout the trial. Any DLT must be reported to the sponsor within 24 hours of first knowledge. Only DLTs occurring during cycle 1 will be used for MTD determination. All relevant safety information (including DLTs occurring at any time) will be considered when selecting the RD.

Severity of AEs will be graded according to CTCAE Version 5.0. Any of the following AEs will be classified as DLTs following review by the Investigators and the sponsor, unless unequivocally due to underlying malignancy or an extraneous cause.

Haematologic toxicities:

- Any Grade 5 toxicity
- Neutropenia \geq Grade 4 lasting for >7 days
- Febrile neutropenia of any duration (ANC $<1.0 \times 10^9$ cells/L and fever $\geq 38.5^{\circ}\text{C}$)
- Neutropenia \geq Grade 3 with documented infection
- Grade 4 thrombocytopenia, or Grade 3 thrombocytopenia with bleeding
- Thrombocytopenia of any Grade which requires platelet transfusions
- Grade 4 anaemia unexplained by underlying disease
- Anaemia of any Grade which requires blood transfusions

Non-haematological toxicities:

- AST or ALT >3 times ULN and concurrent total bilirubin >2 times ULN without initial findings of cholestasis (e.g., findings consistent with Hy's law or the FDA definition of potential DILI, see section [5.2.6.1.4](#))
- \geq Grade 4 AST or ALT of any duration
- Any \geq Grade 3 non-haematologic toxicity with the following exceptions:

Proprietary confidential information © 2021 Boehringer Ingelheim International GmbH or one or more of its affiliated companies

- Grade 3 irAE that resolves to \leq Grade 1 or to baseline with immunosuppressive therapy within 2 weeks
- Grade 3 fatigue that persists \leq 7 days
- Grade 3 rash that resolves to \leq Grade 1 within 2 weeks
- Grade 3 or 4 elevation in serum amylase and/or lipase that is not associated with clinical or radiographic evidence of pancreatitis
- Grade 3 electrolyte abnormality that lasts <72 hours, is not clinically complicated, and resolves spontaneously or responds to conventional medical intervention
- Grade 3 nausea or vomiting that lasts <48 hours, and resolves to \leq Grade 1 either spontaneously or with conventional medical intervention
- Alopecia
- Grade 3 endocrine disorders (thyroid, pituitary, and/or adrenal insufficiency) that are managed with or without systemic corticosteroid therapy and/or hormone replacement therapy, and the patient is asymptomatic.
- Grade 3 tumour flare syndrome
- Grade 2 pneumonitis of any duration
- Grade 2 related uveitis, eye pain, or blurred vision that does not respond to topical therapy and does not improve to Grade 1 severity within 2 weeks or requires systemic treatment
- Treatment pause of BI 891065 for \geq 7 days in Cycle 1 due to treatment-related AEs
- Any treatment-related \geq Grade 2 toxicity that persists and results in a more than 2 weeks delay of administration of BI 754091 on Cycle 2 Day 1
- Any AEs that require dose reduction will be assessed by SMC and may be considered as DLTs unless the SMC considers the dose reduction as not strictly medically warranted
- Permanent treatment discontinuation according to section [4.1.6](#)

The frequency, time to onset, and severity of toxicities, as well as the success of standard medical management and dosing interruptions/delays, will be analysed to determine if a given toxicity should be considered a DLT for dose escalation purposes.

Late DLTs are AEs that meet the same grading criteria as DLT criteria but occur after the first cycle of study treatment. In order to assess the recommended dose, the BLRM will be rerun using all DLTs up until 90 days after the first administration of the last patient.

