3. DESCRIPTION OF DESIGN AND TRIAL POPULATION

3.1 OVERALL TRIAL DESIGN AND PLAN

This is a Phase I, open-label, non-randomised, multicentre trial of BI 891065 given as single agent (Part A) and in combination with BI 754091 (Part B). The data obtained from the trial will determine the MTD estimate for each Part based on a Bayesian logistic regression model (BLRM) with overdose control ([R13-4803](#)). The BLMR estimates the MTD by updating estimates of the probability of observing a DLT in the MTD evaluation period for each dose level in the trial as patient information becomes available. At any time in the trial, it will not be permitted to escalate to a dose which does not fulfil the EWOC principle (refer to section [7](#)). Dose-escalation will be restricted to a maximum of 100 % from the previous dose.

In Part A, successive cohorts of patients will receive increasing doses of BI 891065. The starting dose of BI 891065 is 100 mg once daily. The dose escalation continues until the MTD is reached, or the safety in the highest planned dose level (400 mg total daily dose of BI 891065) is confirmed. Depending on the occurrence of DLTs or other relevant safety information, SMC may decide to decrease the dose of BI 891065. For any dose-escalation cohort, at least three patients will be enrolled. SMC may decide enrolment of further patients. However, in the case that only two patients are evaluable (i.e. one patient is not evaluable) and neither has experienced a DLT within the MTD evaluation period, then dose-escalation can occur based on these two patients.

A Safety Monitoring Committee decides the size for the next dose escalation cohort. After all patients in a cohort have either experienced a DLT or have been observed for at least the MTD evaluation period without experiencing a DLT, the BLMR will be updated with the newly accumulated data. The overdose risk will then be calculated for each dose, and escalation will be permitted to all doses which fulfil the EWOC criterion and the additional 100 % escalation rule. Based on the model and on other available information, the members of the SMC will reach a joint decision on the next dose level to be investigated.

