6. GENERAL ANALYSIS DEFINITIONS

6.1 TREATMENT(S)

In Part A of this Phase I trial, treatments are not randomized. Different dose levels and dose schedule of BI 891065 monotherapy are being administered.

The data will be presented only for Part A, because Part B was cancelled, as mentioned earlier.

For safety summaries events that start from the first administration of any trial medication until 30 days (REP) after the last administration of any trial medication will be considered as having occurred “on-treatment”. If not specified otherwise, all safety tables will be based on the on-treatment period. Adverse events that have onset during the screening or the follow-up period will be displayed in separate listings from those that occurred during the on-treatment period. The MTD evaluation period will be defined as the period from 1st treatment administration (day 1) till day 21 inclusively.

Labels of each treatment period, the labels used for displays in the tables and listings in the CTR, as well codes, decodes, sort order and labels for each trial medication are provided in the TSAP technical documents.

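### A treatment-related pause of BI 891065 starting on days 16–21 cannot meet the cycle-1 pause criterion, so the patient can enter the BLRM as DLT-free

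*Protocol*

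**What the plan says.** Protocol 2.1.1 defines the MTD evaluation period as the first 21-day cycle. SAP 6.1 fixes its end: "The MTD evaluation period will be defined as the period from 1st treatment administration (day 1) till day 21 inclusively". Protocol 4.1.7 states that "Only DLTs occurring during cycle 1 will be used for MTD determination".

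Two criteria in 4.1.7 that apply to Part A matter here:

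- **Pause.** A pause of BI 891065 is a DLT if it lasts at least 7 "days in Cycle 1 due to treatment-related AEs". The cycle limit is attached to the duration.
- **Eye toxicity.** Related Grade 2 uveitis, eye pain or blurred vision is a DLT if it does not respond to topical therapy and "does not improve to Grade 1 severity within 2 weeks or requires systemic treatment". No cycle is named.

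Protocol 3.1 updates the BLRM once every patient in the cohort has had a DLT or they "have been observed for at least the MTD evaluation period without experiencing a DLT". Nothing there delays the update for an event still in progress. Under 3.3.4.1, missing more than 5 doses makes a patient non-evaluable only if the cause is something other than a treatment-related AE.

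**The concern.** A duration rule confined to a fixed window has a blind period at the end of that window. Here the blind period begins about when scheduled cycle-1 assessment ends: the Flow Chart places the last two cycle-1 visits nominally on days 15 and 16. If drug is taken on day 15 and a finding at that visit leads to a pause from the next day, the pause already cannot qualify.

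The cycle-1 DLT count is a primary endpoint and is the input to the overdose-control (EWOC) rule. If a toxicity long enough to satisfy the criterion is recorded as no DLT only because of its start day, the count is too low and the model may allow a dose it would otherwise have ruled out.

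**Working it through.** **1. Pause criterion.** A pause starting on day s and continuing to the end of the window contributes 21 − s + 1 = 22 − s days inside cycle 1. The criterion needs 22 − s ≥ 7, so s ≤ 15. At s = 16 the count is 6; at s = 21 it is 1. Starts on days 16–21 cannot qualify: 6/21 = 29% of calendar days.

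**2. Does the patient stay evaluable?** Yes. The missed-dose rule in 3.3.4.1 does not apply to doses missed for treatment-related AEs. The rule on dose reduction in the first cycle does not apply either: a pause starting on day 16 that lasts 7 full days ends on day 22, so any restart at a lower dose falls after cycle 1.

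**3. Which events are exposed?** Those for which Protocol 4.1.6 pauses drug, or allows a pause, but which 4.1.7 does not list as DLTs in themselves. Examples are Grade 3 neutropenia without fever or infection, and Grade 2 AEs judged intolerable.

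**4. Eye criterion.** Counting two weeks as elapsed time, onset day t must satisfy t + 14 ≤ 21, so t ≤ 7. Counting 14 days inclusively, t + 13 ≤ 21, so t ≤ 8. If the criterion had to be fulfilled by day 21, onsets on 13 or 14 of the 21 days (62% or 67%) could not complete it unless systemic treatment was given. If onset decides, none are lost. The text does not choose between these readings.

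**5. Effect of one uncounted DLT.** I first reproduced the plan's figures. Inputs were the Part A mixture prior of Table 7.1.1: 2, the 200 mg reference dose, the logistic model of 7.1.1 and a binomial likelihood, integrated on a grid. All 12 scenarios of Table 10.4.1: 1 agree within 0.012, with the same next dose. P(OD) is the posterior probability that the DLT rate is at least 0.33; EWOC requires it to be below 0.25.

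| Data | P(OD), plan | P(OD), grid | Model's next dose |
|---|---|---|---|
| 0/3 at 100, 0/3 at 200, 3/6 at 400 mg | 0.413 at 400 mg | 0.411 | 200 mg |
| same, 2/6 at 400 mg | 0.134 at 400 mg | 0.135 | 400 mg |
| 1/3 at 100, 1/3 at 200 mg | not given at 400 mg | 0.303 at 400 mg (fails EWOC) | 200 mg |
| 1/3 at 100, 0/3 at 200 mg | not tabulated | 0.081 at 400 mg (passes) | 400 mg |

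The last two rows start from 1/3 at 100 mg, the result that Table 7.1.2: 1 reports for Part A of this trial; the 200 mg results are hypothetical.

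The decision does not always change. Table 10.4.1: 1 has eight pairs of scenarios that differ by one DLT at the last dose. The next dose changes in three (2 v 3, 5 v 6, 10 v 11) and is the same in five (1 v 2, 4 v 5, 8 v 9, 9 v 10, 11 v 12).

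**The case against.** A reader might infer that all the 7-day and 2-week rules fail for late onsets and that the DLT count is therefore generally biased towards safety. The documents do not support that:

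- **Grade 3 irAE, rash and fatigue.** Duration is an exception to a default DLT. A late event not yet resolved has not earned the exception and stays a DLT. Any bias there runs the other way.
- **Grade 4 neutropenia.** The criterion reads "Grade 4 lasting for >7 days", but 4.1.6 lists drug-related AEs of Grade 4 or above for permanent discontinuation, and 4.1.7 makes such discontinuation a DLT. A related event is caught without waiting for the duration.
- **The BI 754091 delay.** A toxicity that "results in a more than 2 weeks delay of administration of BI 754091 on Cycle 2 Day 1" can only be confirmed after day 21. Its presence in the list favours attribution by onset, as does the definition of late DLTs in 4.1.7, which turns on when the AE occurs. Part B was cancelled in any case (SAP 3).

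There are also safeguards. Day 21 is a minimum observation time. Section 4.1.7 provides for review of onset and dosing interruptions when deciding what counts as a DLT for escalation, and refers AEs requiring dose reduction to the SMC. The SMC also weighs other information.

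All of this stands, and it confines the point to the pause criterion and the undefined attribution of the eye criterion. It does not remove the point. The review is discretionary and gives no dating rule. The BLRM rerun on DLTs from all cycles comes after escalation and, read literally, cannot recover a pause whose length is counted only in cycle 1. One could argue that a delayed cycle 2 lengthens cycle 1, but 2.1.1 and SAP 6.1 both fix the period at 21 days.

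**Conclusion.** The point holds for the pause criterion: a treatment-related pause starting on days 16–21 cannot be a DLT under it, and the patient enters the BLRM as DLT-free unless another criterion or the discretionary review applies. For the eye criterion the plan is silent on onset against fulfilment, and no text holds the update for an open event.

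The 29% is a share of calendar days. It would be a miss probability only if pause starts were uniform over the cycle, and the documents give no onset data. The consequence is conditional: one uncounted DLT reverses the model's recommendation in some constellations and not in others. The figures describe the model alone, not an SMC decision. The documents do not report whether any such pause occurred.

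**What to change.** Reconcile Protocol 3.1 and 4.1.7 with SAP 6.1 on three points:

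1. Attribute a DLT to the MTD evaluation period by AE onset, or by the start of the pause, within days 1–21, even if its duration criterion is completed later.
2. Let the cycle-1 limit qualify the start of the pause, not its length. Simply deleting the limit would turn pauses in later cycles into DLTs in the rerun on all cycles.
3. Do not enter a patient as DLT-free while an event that could still meet a duration criterion is open.

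The cost is wording and an occasional wait. A pause starting on day 21 reaches 7 days on day 27, about a week after the window closes. An eye event starting on day 21 is settled by day 35, so at most two weeks later.

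Protocol 11.4 records the primary endpoint assessments as complete, so new wording cannot alter escalation decisions already taken. It would still settle which events count in the first-cycle BLRM evaluation that SAP 7.4.1 plans for the trial report. Checking the cycle-1 dosing records for pauses starting on days 16–21 would show whether the count is affected.
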